## Abstract

**Introduction:** Pregnancy is a period of profound physiological and emotional transformation, often leading to heightened **anxiety** due to hormonal shifts, body image changes, and the anticipation of motherhood. This anxiety can significantly impact both maternal and fetal well-being. Recognizing the need for effective interventions, non-pharmacological approaches like **music therapy** are gaining traction due to their low risk of side effects. This study highlights the historical use of music for relaxation and its ability to influence physiological responses, such as hormone release. Specifically, it introduces the **Sape' Dayak**, a traditional Indonesian instrument known for its calming qualities, as a potential therapeutic tool. While Sape' music has cultural significance, its specific efficacy in reducing anxiety in pregnant women remains under-researched.

**Objectives:** This study attempts to address the gap by investigating whether Sape' Dayak music can reduce anxiety levels in pregnant mothers as successfully as traditional lullabies, therefore promoting holistic health practices and maintaining cultural heritage.

**Methods:** Thirty-two pregnant women will be recruited from midwifery clinics. A total of 16 pregnant women will receive the traditional Sape' Dayak music, while another 16 pregnant women will undergo the lullaby music therapy. Following a non-randomized design, we will collect data on an anxiety assessment using the PASS before and after the music intervention. Data will be analysed using the linear mixed model.

**Keywords:** anxiety, pregnancy, music therapy, lullabies, traditional music, mental health

## 1. Introduction

A woman's life undergoes significant transformation during the gestational period, which is characterized by a symphony of physiological and emotional adaptations designed to support the growing fetus (1). These substantial changes could have far-reaching effects, affecting not only the woman's physical health but also her emotional and psychological stability (2). The increase of hormones, the changing perceptions of body image, and the expectation of motherhood together create a unique emotional environment, resulting in pregnant women possibly being more susceptible to increased levels of anxiety (3). This sensitivity is worsened by worries about the pregnancy, the fetus's health, and the labor and delivery process. Anxiety during pregnancy is a common experience, frequently arising from the numerous uncertainties and challenges associated with this phase of life, and it can have significant repercussions, affecting both the mother and the developing child (4). The occurrence of anxiety disorders during pregnancy highlights the necessity for effective intervention strategies, particularly considering the potential long-term effects on both maternal and offspring well-being (5).

Diverse therapeutic approaches have emerged in response to the urgent need for successful solutions, including psychosocial support, alternative therapies, and pharmacological interventions. There is an increasing interest in non-pharmacological interventions, like music therapy, which have shown effectiveness in alleviating anxiety and fostering relaxation during pregnancy (6). Non-pharmacological interventions are especially attractive because they carry a low risk of negative side effects for both the mother and the developing fetus. Music therapy has become acknowledged as a gentle and approachable method that can successfully reduce anxiety and promote relaxation during pregnancy. Mindfulness-based approaches are preferred for managing stress and improving well-being during pregnancy (7). Relaxation techniques are essential for minimizing or preventing the potential negative impacts of maternal stress (8). In addition to standard therapeutic methods, there is increasing acknowledgement of the advantages of traditional cultural practices, including lullabies and traditional songs, for improving maternal well-being during pregnancy.

According to Ni Gusti Made Ayu Agung Budhi and Sasnitia (9), music therapy is a non-pharmacological method that can help with pain relief, stress reduction, and anxiety reduction, particularly during childbirth. This is true regardless of the mother's age, education level, religion, socioeconomic status, number of children, or social support. Music has been utilized as a means of relaxation since ancient times, with historical evidence indicating its presence

across various cultures. It is known to generate positive sensory stimuli that can trigger endorphin release (10). Music influences the parasympathetic nerve and autonomic nervous system, either directly or indirectly (10). Listening to music exerts a soothing and uplifting effect on individuals and positively influences unborn babies. The beneficial sound from music facilitates prenatal stimulation, aiding pregnant mothers in bonding with their unborn children (11). Music can influence hormone release, as relaxing music has been shown to reduce cortisol levels and may also affect other hormones associated with stress and well-being. Research indicates that family-centered music therapy positively impacts the well-being of parents and infants in neonatal intensive care units (12). Music during labor correlates with reduced pain and anxiety levels, along with lower postpartum analgesic needs (13).

With its origins in cultural history, traditional music contains unique rhythmic patterns and aural structures that may influence both mental and physical states, making it a desirable choice for treating anxiety. Traditional music serves as a tool for alleviating anxiety symptoms and promoting relaxation through the integration of culturally relevant sounds in therapeutic environments (14). Known for its gentle, contemplative sounds, the Sape is a traditional Dayak musical instrument from East Kalimantan, Indonesia. The Sape' has historically been integral to Dayak healing rituals, spiritual offerings, and community entertainment. It conveys family history and cultural values as a sign of Dayak identity. With its delicate tones and repeating rhythms, the Sape' creates pentatonic melodies that promote healing and relaxation while fostering a calm, reflective, and emotionally calming environment. The cultural significance is well-established, and there is increasing acknowledgment of its potential therapeutic benefits, particularly in reducing anxiety. Because pregnancy frequently causes increased anxiety, research into non-pharmacological techniques like music therapy—like those utilizing the Sape'—is essential for the well-being of expectant mothers. Thus, examining the potential of Sape' Dayak to reduce anxiety in expectant mothers advances the study of holistic health therapies as well as the preservation of cultural heritage.

Discussions on the Sape' Dayak in academia and culture today mostly center on its cultural value, gender roles in its performance, and its changing position in modern society. A significant gap remains in the research on the therapeutic applications of Sape' music. Particularly, there is a scarcity of research that investigates the potential of traditional Dayak music, including the Sape', to enhance mental health, particularly in the context of maternal health, by reducing anxiety. This gap signifies an overlooked opportunity to integrate cultural

heritage with modern healthcare practices. While Nadia Anjani, Amir Razak (15) propose that Sape' music possesses anxiety-reducing properties, this claim necessitates additional empirical investigation, particularly in specific populations such as expectant women.

This study seeks to examine the efficacy of Sape' Dayak music in alleviating anxiety among pregnant women. The primary goals are to ascertain whether the anxiety levels of expectant women are similarly influenced by exposure to Sape's Dayak music as they are by conventional lullaby instruments.

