## **2. Materials and Methods**

### *2.1. Study design*

This study is a quasi-experiment with a control group and is conducted in alignment with the JBI standard, published in 2020 (16). Pre- and post-tests are conducted to assess the effects of the music therapy.

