### *2.2. Study participants*

This study will involve 32 pregnant women who will receive standard antenatal care (ANC). All of them are ANC visitors at midwifery clinics between 1 February and 30 April 2025. A total of 16 pregnant women will receive the traditional Sape' Dayak music, while another 16 pregnant women will undergo the lullaby music therapy.

Participants will be recruited during their third trimester of pregnancy (28-40 weeks). They will be eligible if they are 1) at least 18 years old, 2) having a score on the Pittsburgh Sleep Quality Index (PSQI)  $> 5$ , which indicates poor sleep quality, and 3) primiparous. Exclusion criteria included women who 1) are beyond the 40th week of pregnancy; 2) have mental illness that causes hallucinations or altered perception of reality; or 5) have a twin pregnancy.

Sample size is estimated by applying these parameters as follows: The effect size is considered to be 0.52 (17), with a power of 0.8 and a 0.05 level of significance. Sample size calculations for comparing the two independent means (18) indicates each group requires 14 participants. For dropout anticipation, we add an extra 10% of participants. Two participants are withdrawing due to preterm delivery (n=2). The test power is maintained by recruiting new participants.

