### *2.3. Procedures*

During the study period, trained assistants will approach potential pregnant women who attend midwifery clinics, and the 32 women are assessed for eligibility for the study by the research assistant. Firstly, women who will meet the inclusion criteria will be informed of the aim and content of the study, and their written informed consent will be obtained prior to the experiment. After inclusion in the study, participants ( $n = 32$ ) will be purposefully allocated, with the rules that those who visit midwifery clinic A will be grouped in the intervention group (IG) ( $n = 16$ ), while the control group (CG) ( $n = 16$ ) will be made up of those who visit midwifery clinic B. The distance between clinics is 15 km, which minimizes interactions between participants in the two groups. The IG will listen to Sape' Dayak while gently massaging their abdomens and imagining their infants. The lullaby of Brahms will be played for the CG, who will also touch gently on the tummy and remind of their unborn children. Each piece of music will be performed for 20 minutes. Respondents will be instructed to wear earphones to listen to the music. The experiment will be conducted between 08:00 and 11:00 post-breakfast, during which no medical care, diagnostic assessments, or normal follow-ups are performed. Throughout the experiment, they will maintain standard care and treatments. The main investigator at the clinic will manage all practices that could potentially influence the study.

The participants will not interact with the researchers administering the intervention unless they receive important information about the experiment to minimize confounding effects on the research outcomes. The intervention will be conducted by the same assistant. The assistants and participants will not be blinded to the research given the characteristics of the music intervention. To avoid patient interaction between the two groups, the intervention will be carried out in each pregnant woman's home while she is comfortably seated in a chair in her room.

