For three consecutive days, the IG will utilize a music device to listen to the Sape' Dayak for 20 minutes each day. The Sape' Dayak has a slow rhythm (the beat fluctuates from 80 to 85 beats per minute, measured by a metronome), which corresponds to the normal heart rate. Each participant will receive an earphone. Evidence has shown that listening to music for relaxation therapy can last practically from 10 to 60 minutes (19-23). In accordance with the findings of the study, a length of 20 minutes will be established. Respondents will be directed to compile a personal preference playlist for relaxation, which will be subsequently saved on the paid Spotify platform. Participants will be instructed to listen to the lullaby while reflecting on their babies and engaging in physical connection by touching their abdomen. The intervention will be conducted in the participants' homes, at times when they will be available and feel prepared. The door and windows of the room will be closed to ensure the participants' privacy. Participants will be instructed to have an empty bladder, turn off their cell phones, and refrain from receiving medical treatment during the intervention. Respondents in the CG will be directed to listen to Brahms' lullaby following the same procedure.

To ensure participants compliance, the Trackify music tracking app will be used, and research assistants will collect the time of playing from the app upon completion of the session.

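### The protocol states an efficacy aim for Sape' music and reads the effect of music from pre- and post-tests, but both arms get music in the same session, so the design estimates only Sape' relative to lullaby

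*Protocol*

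**What the plan says.** The closing paragraph of the protocol's Introduction makes two statements of purpose. The first concerns efficacy: "This study seeks to examine the efficacy of Sape' Dayak music in alleviating anxiety among pregnant women". The second is comparative, set against conventional lullabies: "The primary goals are to ascertain whether the anxiety levels of expectant women are similarly influenced by exposure to Sape's Dayak music". The Abstract's objective combines them by asking whether Sape' music can lower anxiety as well as lullabies do, which presupposes a reduction. Section 2.1 calls the study a quasi-experiment with a control group and says: "Pre- and post-tests are conducted to assess the effects of the music therapy".

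The two groups are described as follows.

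- Arms (Section 2.2): "A total of 16 pregnant women will receive the traditional Sape' Dayak music, while another 16 pregnant women will undergo the lullaby music therapy".
- Sape' session (Section 2.3): "The IG will listen to Sape' Dayak while gently massaging their abdomens and imagining their infants".
- Lullaby session (Section 2.3): "The lullaby of Brahms will be played for the CG, who will also touch gently on the tummy and remind of their unborn children".
- Setting for both (Section 2.3): "the intervention will be carried out in each pregnant woman's home while she is comfortably seated in a chair in her room".
- Control procedure (Section 2.4): "Respondents in the CG will be directed to listen to Brahms' lullaby following the same procedure".

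Sessions last 20 minutes a day for three days in a row (Section 2.4). PASS is taken once before and once after the intervention (Section 2.5). Women and assistants are not blinded, and clinic attended decides the group (Section 2.3).

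**The concern.** An efficacy statement about Sape' music needs a contrast in which the music is present on one side and absent on the other while the rest of the session stays the same. The protocol has no such contrast. What it calls the control group is a second music group.

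If PASS falls by a similar amount in both groups, the Abstract, Introduction and Section 2.1 read together invite the report that Sape' music reduces anxiety, and does so as well as a lullaby. The same data would arise if neither piece did anything and the fall came from quiet rest, touch, imagery, expectation, answering the questionnaire again, or the passage of three days in late pregnancy. A claim of benefit in pregnant women would then rest on a change that the design cannot attribute to the music.

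**Working it through.** The protocol gives no figure for this point. Its one computed figure, 14 women per group in Section 2.2, does not enter the argument. The check is therefore a matter of what each available contrast contains.

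**Step 1. Write out the change in each group.** Let S and L be the effects of Sape' and of lullaby music against the same session without music. Let N be everything the sessions share: touch, imagery, seated rest, expectation, retesting and time. Let A and B be whatever differs between women of clinic A and clinic B. For simplicity, take the parts as additive.

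- Change in Sape' group = S + N + A
- Change in lullaby group = L + N + B

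**Step 2. Take the contrasts that the data allow.**

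- Within the Sape' group: S + N + A. The music effect S cannot be separated from N, because no group or period supplies N alone. The single pre-test precedes the music but gives a level, not an untreated change.
- Between groups: (S − L) + (A − B). N cancels, and so does any effect that the two pieces have in common. What remains is Sape' relative to lullaby, plus the difference between clinics.

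**Step 3. Look at equal falls.** If both groups change by the same amount and A = B, then S = L. That holds when S and L are both large and equally when both are zero.

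**Step 4. Give a sense of size.** The protocol offers no estimate of N, so it is assumed. Suppose S = 0 and A = 0, and let the non-music change be d standard deviations of the change score. A two-sided paired t-test at 0.05 with n = 16 has 15 degrees of freedom and noncentrality d × √16 = 4d.

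| Assumed non-music change d | Noncentrality 4d | Probability of a significant within-group change |
|---|---|---|
| 0.2 | 0.8 | 0.12 |
| 0.3 | 1.2 | 0.20 |
| 0.5 | 2.0 | 0.46 |
| 0.8 | 3.2 | 0.85 |

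With no non-music change the probability would be 0.05. The table illustrates what happens if the within-group change is read as the effect of music. Section 2.6 does not plan such a test.

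**The case against.** The best defence is that the study is comparative. The Introduction labels the comparison with lullabies as the primary goal, the efficacy sentence can be read as a lead-in, Section 2.1 names a control group, and Section 2.2 sizes the study for two independent means. An active music comparator is a legitimate choice for that goal. This stands, and it limits the point to the efficacy aim and the pre/post attribution.

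It is also true that Section 2.6 names no paired test and no rule for concluding efficacy. It lists between-group tests for anthropometric and confounding variables, tests for categorical variables, and a linear mixed model. The misreading described above is therefore an inference from the wording of the aims, not a planned analysis. The wording still has to be put right, because no analysis can recover a contrast that was not collected.

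A reader might go further and infer that efficacy would stay out of reach even with randomisation and a margin. The documents do not support that. In a randomised trial, superiority of Sape' over lullaby would show efficacy if lullaby does no harm, and a margin justified from lullaby's effect against no music could support efficacy indirectly. The protocol makes neither argument. It cites a randomised lullaby study, by its title in high-risk pregnancy, only for the effect size of 0.52.

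A reader might also take Section 1's remark on relaxation techniques as proof that touch and imagery act. It names neither, and Section 2.4 treats music listening itself as relaxation therapy. Section 2.3 also limits contact between participants and the researchers giving the intervention, so attention from staff should not be pressed as an explanation.

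**Conclusion.** The point holds for the efficacy aim in the Abstract and Introduction and for the pre/post statement in Section 2.1. It does not hold against the comparative goal or the choice of an active comparator.

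The design estimates Sape' relative to lullaby, subject to allocation by clinic. The split of a within-group change between music and everything else is not identified. Under assumed non-music changes of 0.2 to 0.8 SD, a within-group test with 16 women would be significant with probability about 0.12 to 0.85 with no music effect at all. That range rests on the assumed changes and not on any figure in the protocol. The conclusion that music is not isolated does not depend on it.

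Nothing here shows that Sape' music is ineffective. The finding is only that this design cannot credit it with a fall in PASS.

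**What to change.** 1. In the Abstract's objective and the last paragraph of the Introduction, replace the efficacy wording with the contrast that the design contains: *to estimate the difference in PASS change between Sape' sessions and Brahms lullaby sessions, each with abdominal touch and thinking of the baby.*
2. In Section 2.1, replace the statement that the pre- and post-tests assess the effects of music therapy with: *PASS is measured before and after the sessions so that change can be compared between groups. Within-group changes are descriptive and will not be reported as evidence that Sape' music reduces anxiety.*

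The cost is a narrower headline claim. Procedures, sample size and planned analyses are untouched.

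A music-free run-in for each woman is not advised as a repair. In a fixed order it would confound music with period, and it adds procedures.

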## *2.6. Data analysis*

All statistical analyses will be conducted employing the IBM SPSS v.26 statistics software (SPSS Inc., Chicago, USA). The alpha level will be set up at  $p < 0.05$  (two-tailed). A descriptive analysis of the major study variables will be conducted. For the quantitative numeric, the means, standard deviations, and confidence intervals will be computed. The Shapiro-Wilk test will be employed to assess data normality. The student's t-test will be employed to analyze differences between groups for anthropometric and confounding variables. The medians, maxima, and minima will be applied when the distribution is non-normal. In addition, the chi-square test or Fisher's exact test will be used for categorical variables. Multivariate analysis will be carried out with a linear mixed model for additional analysis.

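### The primary objective asks whether Sape' works similarly to the lullaby, but the trial is sized for a difference and states no margin, so a non-significant result would leave that question unanswered

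*Protocol*

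**What the plan says.** **Objective.** The Introduction gives as the primary goal whether "anxiety levels of expectant women are similarly influenced by exposure to Sape's Dayak music as they are by conventional lullaby instruments". The Abstract asks whether Sape' can "reduce anxiety levels in pregnant mothers as successfully as traditional lullabies". The Introduction also names a general aim of examining the efficacy of Sape', but both groups listen to music and there is no group without it.

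**Sample size.** Section 2.2: "The effect size is considered to be 0.52 (17), with a power of 0.8 and a 0.05 level of significance". It continues: "Sample size calculations for comparing the two independent means (18) indicates each group requires 14 participants". With the 10% dropout allowance this becomes 16 per group.

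**Analysis.** Section 2.6: "The alpha level will be set up at" 0.05, two-tailed. The t-test is assigned to anthropometric and confounding variables, and a linear mixed model is listed as an additional analysis. The Abstract is firmer: "Data will be analysed using the linear mixed model". PASS is measured before and after the intervention; section 2.1 says "Pre- and post-tests are conducted to assess the effects of the music therapy".

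No equivalence or non-inferiority hypothesis, no margin, and no rule for judging a confidence interval against a margin is stated.

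**The concern.** A question about similarity needs a statement of how large a difference would still count as similar, and a result that could rule out anything larger. The protocol has neither. Its sample size and its two-tailed level belong to a test whose null hypothesis is no difference. Failing to reject that null is not evidence for it, least of all with 16 women per group.

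What is at stake is the trial's main conclusion. Two equally effective pieces of music would give p>0.05 in 95% of trials. A clearly less effective Sape' could also often give p>0.05. Without a rule, that result may be written up as an answer to the stated objective.

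**Working it through.** **1. Objective against design.**

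| Result of a two-sided difference test | Similar (Introduction) | As successful as (Abstract) |
|---|---|---|
| Significant, Sape' worse | contradicted | contradicted |
| Significant, Sape' better | contradicted | supported, as at least as successful |
| Not significant | undecided | undecided |

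No row supports similarity. This step needs no assumed figure.

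**2. The plan's own figure.** Inputs from section 2.2: effect size 0.52, power 0.8, alpha 0.05; two-sided from section 2.6. Reading 0.52 as a standardised mean difference d:

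n per group = 2 × ((1.960 + 0.842)/0.52)² = 58.05, so 59 (60 by the t distribution).

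The stated 14 does not reproduce. If 0.52 is Cohen's f, then d = 2 × 0.52 = 1.04 and n = 2 × (2.802/1.04)² = 14.5, so 15 (16 by t), which is close. The protocol does not name the metric, so both readings are carried below. Whether 14 is right is a separate matter.

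**3. How often would p>0.05 occur if Sape' were truly worse?** Take 16 per group, two-sided 0.05 and noncentral t, with noncentrality (d/k) × √(16/2):

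- unadjusted: k = 1, 30 degrees of freedom;
- baseline-adjusted: k = √(1 − ρ²), 29 degrees of freedom;
- change score (group-by-time): k = √(2(1 − ρ)), 30 degrees of freedom.

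The pre-post correlation ρ of PASS is not given. Values of 0.5, 0.8 and 0.9 are assumed. A high value is possible because the intervention is short (section 2.4: "For three consecutive days, the IG will utilize a music device"). For the unadjusted case at d = 0.52, the noncentrality is 0.52 × √8 = 1.471, the critical value is 2.042, and P(p>0.05) = 0.704.

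| Analysis | P(p>0.05), d = 0.52 | P(p>0.05), d = 1.04 | 95% CI half-width (SD) |
|---|---|---|---|
| Unadjusted | 0.704 | 0.188 | 0.722 |
| Adjusted, ρ = 0.5 | 0.625 | 0.093 | 0.626 |
| Adjusted, ρ = 0.8 | 0.341 | 0.003 | 0.434 |
| Adjusted, ρ = 0.9 | 0.097 | <0.001 | 0.315 |

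For the change score at d = 0.52, the figures are 0.704, 0.386 and 0.111. Half-width = critical t × k × √(2/16). The adjusted rows assume equal baseline means.

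**4. What if a margin were stated?** The documents give none, so 0.52 SD is used purely as an illustration. The test is non-inferiority, one-sided 0.025, with a true difference of 0.

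| Analysis | Power at 16 per group | n per group for 80% | Smallest margin with 80% power at 16 per group (SD) |
|---|---|---|---|
| Unadjusted | 0.296 | 60 | 1.02 |
| Adjusted, ρ = 0.5 | 0.375 | 45 | 0.89 |
| Adjusted, ρ = 0.8 | 0.659 | 22 | 0.62 |
| Adjusted, ρ = 0.9 | 0.903 | 13 | 0.45 |

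**The case against.** **Some result could still be positive.** A reader might infer that no planned result can support the objective at all. That goes too far. The Abstract's wording runs in one direction, and a significant result favouring Sape' would support at least as successful. It would not support the Introduction's similarity.

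**The PASS test is not spelled out.** This is fair. Section 2.6 does not attach a hypothesis test to PASS, so testing for a difference is inferred from the two-means sizing and the two-tailed level. The section also plans confidence intervals, but as descriptive statistics for numeric variables, not for the group difference. The missing margin is unaffected.

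**An SAP could add a margin.** It could, and a margin fixed before data are seen gives a valid test. The sample size governs only its power, which at 16 per group is good if ρ is near 0.9 and poor if the analysis is unadjusted. The documents do not support saying that a later margin cannot repair the plan. But the protocol itself pairs a similarity objective with a sample size set for a difference, and that mismatch stands whatever an SAP adds.

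**The 70% is the pessimistic end.** Also fair. It is the unadjusted figure, whereas the model named for pre/post PASS can use baseline. It also depends on reading 0.52 as a standardised difference. A reader might likewise infer that the 1.02 SD margin is twice the trial's own design difference; under the Cohen's f reading it is about equal to it.

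**The protocol never says p>0.05 will be read as similarity.** Correct, and no such intention should be attributed to it. The fault is that the objective is similarity and nothing blocks that reading.

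**Conclusion.** The point holds. The stated primary objective is similarity, the design is for a difference, and there is no margin. That follows from the text alone. A significant difference would contradict similarity, and a non-significant one would be inconclusive.

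How misleading a non-significant result could be depends on two things the protocol does not give, the metric of 0.52 and the pre-post correlation of PASS. If Sape' is 0.52 SD worse, p>0.05 would occur about 70% of the time unadjusted, and 62%, 34% or 10% with baseline adjustment at correlations of 0.5, 0.8 or 0.9. If 0.52 is Cohen's f, the unadjusted figure is 19%, but that refers to a difference of about 1 SD. Confidence is high in the mismatch and lower in any single percentage.

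**What to change.** **Recommended, text only.**

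- Abstract and Introduction: restate the primary objective as estimating the between-group difference in PASS (Sape' minus lullaby), taking baseline PASS into account, with its 95% confidence interval.
- Section 2.6: name this difference as the main result, taken from the linear mixed model already planned, and state that p>0.05 will not be read as similar or as successful as.
- Section 2.2: state that the sample size concerns detection of a difference and was not set to show similarity.

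This needs no extra women or data. The cost is a more modest conclusion: how large the difference may be, not whether the two are alike.

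**If the similarity objective is kept.** Fix a margin in PASS points before data are seen, and report its power at 16 per group openly. At the illustrative 0.52 SD margin that power runs from 30% unadjusted to 90% at a correlation of 0.9, and 80% power needs between 60 and 13 women per group.

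Neither route removes the confounding that comes from having one clinic per group (section 2.3). The confidence interval describes sampling error only, and the report should say so.
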